2.4 Potential Risks & Benefits

2.4.1 Known Potential Risks

Risks of treatment failure: HCV mutation can lead to drug resistance and treatment failure. In patients administered Mavyret, the risk of this was 2% or less. For patients with treatment resistant HCV, rescue therapy with alternative agents can result in cure of up to 100% depending upon the genotype. Guidelines for the treatment of resistant HCV strains are published and updated regularly. [16]

Risks of treatment intolerance: Over multiple clinical trials. The overall rate of medication related adverse events leading to permanent discontinuation prior to completion of an 8-week course of therapy was 0.1% [17].

Risk of acute hepatitis C infection: Acute hepatitis C is asymptomatic in 66-75% of patients. The risks of acute HCV leading to fulminant hepatic failure are believed to be very low, however case reports of this do exist [18]. To minimize this already very low risk, we are starting treatment in all the patients at the time of transplant before any viremia is even detected.

Risk of chronic hepatitis C infection: Patients who prove refractory to all therapy including rescue therapy and develop persistent viremia are at risk to develop chronic HCV infection, which has the potential to cause cirrhosis/end-stage liver disease, the potential for the need for liver transplantation and/or death. We expect our treatment failure rate in this study to be 0%, therefore we expect the risk of chronic HCV infection to be 0%. In the event of a treatment failure, the risks of developing chronic HCV must be considered. It is estimated that approximately 15-30% of patients with chronic HCV develop cirrhosis/end-stage liver disease over 20-30 years. [19]. This risk should be compared to the risk of death on the lung transplant waiting list. The reported one-year mortality for a waitlisted patient without a transplant is as high 26.7% [20].

The efficacy of HCV treatment with Mavyret is high (98%). The efficacy of rescue therapies approaches 100%. Even in the event of a treatment failure, the risk of cirrhosis and liver disease secondary to chronic HCV are low. We believe that the survival benefit of receiving an earlier lung transplant, by accepting an organ from a HCV-positive donor, far outweighs the risks of HCV exposure and possible treatment failure.

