10.2 Statistical Hypotheses

We hypothesize that 100% of patients who develop HCV viremia will achieve SVR after completing an 8-week course of Mavyret treatment.

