10.4.1 General Approach

The study design will be single arm, open label. Descriptive statistics will include:

- Incidence HCV viremia post-transplant (percentage)
- Time course of exposure to development of clinically detectable viremia in those who develop viremia (median time to viremia with standard deviations)
- Incidence of sustained clearance of HCV (cure) after treatment of viremia (percentage)
- Time course of clearance of viremia after treatment initiation (median time to clearance with standard deviations)
- Incidence of treatment failure/treatment resistant strains of HCV (percentage)
- Characterization of distribution of HCV genotypes in patients who develop viremia (percentages)
Comparison of treatment failure rates to expected treatment failure rates for the treatments used (p value for significance will be set at $p < 0.05$ and two-tailed t-test will be used)

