10.4.3 Analysis of the Secondary Endpoint(s)

Secondary endpoint #1: 1-year patient survival rates in HCV negative lung recipients who receive a lung transplant from a HCV positive donor.

Patients will have regular follow-up as standard of care for all lung transplant recipients. Patients survival will be readily apparent. Furthermore, all deaths of transplant recipients are required to be reported to UNOS.

Secondary endpoint #2: Incidence of HCV viremia among HCV negative recipients who receive a lung transplant from a HCV positive donor.

CONFIDENTIAL

We will be measuring serial HCV RNA Quantitative (PCR) and serologic testing for a minimum of 6-months post-transplant. A patient will be considered to be viremic when a post-transplant HCV RNA Quantitative (PCR) test is positive. The incidence of viremia will be calculated as a percentage of the patients transplanted with a HCV-positive donor who develop HCV viremia by RNA Quantitative (PCR) testing.

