10.5 Sample Size

20 patients are expected to enroll in this trial.

We expect that less approximately 70% of patients will develop evidence of HCV infection transmitted from the HCV-positive donor and will be treated for HCV infection. We expect that 100% of the patients who are treated for HCV viremia will achieve SVR.

This is a single-arm study with no comparison group. The power to detect a difference in observed versus expected depends upon the true efficacy of the therapy. The reported efficacy of the therapy is 98%.

With an estimated 7 patients who will be treated, a single treatment failure will be regarded as a significant deviation from the expected outcome.

CONFIDENTIAL

11 Source Documents and Access to Source Data/Documents

Source data is all information, original records of clinical findings, observations, or other activities in a clinical trial necessary for the reconstruction and evaluation of the trial. Source data are contained in source documents. Examples of these original documents, and data records include: hospital records, clinical and office charts, laboratory notes, memoranda, subjects' diaries or evaluation checklists, pharmacy dispensing records, recorded data from automated instruments, copies or transcriptions certified after verification as being accurate and complete, microfiches, photographic negatives, microfilm or magnetic media, x-rays, subject files, and records kept at the pharmacy, at the laboratories, and at medico-technical departments involved in the clinical trial. It is acceptable to use CRFs as source documents.

If this is the case, it should be stated in this section what data will be collected on CRFs and what data will be collected from other sources.

The study case report form (CRF) is the primary data collection instrument for the study. All data requested on the CRF must be recorded. All missing data must be explained. If a space on the CRF is left blank because the procedure was not done or the question was not asked, write "N/D". If the item is not applicable to the individual case, write "N/A". All entries should be printed legibly in black ink. If any entry error has been made, to correct such an error, draw a single straight line through the incorrect entry and enter the correct data above it. All such changes must be initialed and dated. **DO NOT ERASE OR WHITE OUT ERRORS.** For clarification of illegible or uncertain entries, print the clarification above the item, then initial and date it.

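### No interval is planned for SVR, treatment failure, viremia or one-year survival, so the expected result would read as 100% cure although 14/14 allows up to 23.2% failure and 7/7 up to 41.0%

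*Combined protocol and SAP*

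**What the plan says.** Section 10.1 states that no SAP applies, and Section 10.4 limits the analysis to descriptive statistics. Section 10.4.1 lists the cure result as "Incidence of sustained clearance of HCV (cure) after treatment of viremia (percentage"), and gives viremia and treatment failure as percentages too. The same list plans medians with standard deviations for time to viremia and time to clearance, and a two-tailed t-test at 0.05 of failure rates against expected rates. Section 10.4.2 repeats that the primary endpoint is a percentage. Section 10.4.3 gives one-year survival as a rate, with no estimator or censoring rule, and defines the viremia result: "The incidence of viremia will be calculated as a percentage of the patients transplanted with a HCV-positive donor who develop HCV viremia".

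The hypothesis in Section 10.2 is a point value: "We hypothesize that 100% of patients who develop HCV viremia will achieve SVR after completing an 8-week course of Mavyret treatment". Section 2.4.1 goes further: "We expect our treatment failure rate in this study to be 0%, therefore we expect the risk of chronic HCV infection to be 0" per cent. It does so after putting the risk of treatment failure on Mavyret at no more than 2%.

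On numbers, Section 10.5 says "20 patients are expected to enroll in this trial", then "We expect that less approximately 70% of patients will develop evidence of HCV infection", and later "With an estimated 7 patients who will be treated, a single treatment failure will be regarded as a significant deviation from the expected outcome".

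**The concern.** In a single-arm pilot of 20 patients, precision is the main inferential content that the data can offer, and the plan leaves it out. If every treated patient is cured, as Section 10.5 expects ("We expect that 100% of the patients who are treated for HCV viremia will achieve SVR"), the planned output is 100% and nothing else. A reader could take that as confirming the published efficacy, although so few patients exclude little.

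The protocol means to use these results for comparison. Section 10.4 sets the observed cure rates against those expected in chronic HCV. Section 4.2.2 says the secondary endpoints will help weigh this strategy against staying on the waiting list, for which Section 2.4.1 cites one-year mortality as high as 26.7%. Point estimates without intervals cannot carry either comparison.

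**Working it through.** **Number treated (the plan's own figure).** Inputs from Section 10.5: 20 enrolled, about 70% viremic and treated. 20 × 0.70 = 14, not the stated 7. Other routes do not give 7 either: 20 × 2/3 = 13.3, 20 × 0.30 = 6, 20 × 1/3 = 6.7. Seven is 70% of 10, but no enrolment of 10 appears. Both denominators are therefore carried below.

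**Precision at zero failures.** The exact two-sided 95% upper limit for the failure rate with 0 failures in n is 1 − 0.025^(1/n).
- n = 14: 1 − 0.025^(1/14) = 23.2%, so SVR is 100% (76.8% to 100%).
- n = 7: 1 − 0.025^(1/7) = 41.0%, so SVR is 100% (59.0% to 100%).

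The choice of method matters little. For n = 14 the one-sided exact limit is 19.3%, Wilson 21.5%, and the rule of three 3/14 = 21.4%.

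**The t-test.** A one-sample t statistic divides by s/√n. With no failures every observation is 0, so s = 0 and the statistic is undefined. In the expected case the test adds nothing to the percentage.

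**The 2% reference rate (98% efficacy, Section 10.5).**
- Expected failures: 14 × 0.02 = 0.28, or 7 × 0.02 = 0.14.
- Chance of at least one: 1 − 0.98^14 = 24.6%, or 1 − 0.98^7 = 13.2%.

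An expectation of 0% is therefore not what the protocol's own figure implies. One failure would not be statistically significant at 0.05 for either denominator.

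**Viremia.** The expected 14/20 is 70%, exact 95% interval 45.7% to 88.1%. Now assume (the documents give no dropout rate) that 2 of 20 have no positive PCR because they left or died, and 14 are observed viremic.
- Protocol formula: 14/20 = 70%.
- Both withdraw before any viremia is seen and are censored: 14/18 = 77.8%.
- Best and worst case: 14/20 = 70% and 16/20 = 80%.
- Both die before viremia, with death as a competing event and no censoring: the Aalen-Johansen estimate equals the raw proportion, 14/20 = 70%.

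For 1 and 3 early withdrawals the censored figures are 14/19 = 73.7% and 14/17 = 82.4%. The Section 19 schedule has PCR weekly from POW1 to POW12, then at POW24 and POW52, so leaving with no test at all would take an exit in about the first week.

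**Survival.** With an assumed 18/20 alive at one year and complete follow-up, survival is 90% (68.3% to 98.8%). Mortality is then 1.2% to 31.7%, a range that contains the cited 26.7%.

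**The case against.** The strongest reply is that this is a declared descriptive pilot. The width of the interval comes from the sample size: 76.8% to 100% contains both 98% and 80%, so adding it does not make the trial more informative, and anyone given 14/14 can compute it. The first part stands, because intervals do not add precision. They do show how little precision there is, and a reader cannot recover a survival interval from a percentage when some patients are censored.

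Some stronger readings are tempting, and the documents do not support them.
- A reader might infer that every endpoint is a bare percentage. Section 10.4.1 also plans medians with standard deviations and the t-test, Section 10.4.8 adds individual data, and survival is an unspecified rate that 10.4.1 does not list.
- A reader might infer a stated rule that patients who die or leave are counted as uninfected. There is none. It is a consequence of the Section 10.4.3 denominator, and it concerns viremia only.
- A reader might infer that early deaths bias viremia incidence downward. With death as a competing event, the estimate is the protocol's own 14/20. Only withdrawals can move it.
- A reader might put 2% in place of the 0% chronic-HCV risk in Section 2.4.1. That section ties chronic infection to failure of all therapy including rescue, whereas 2% is failure of Mavyret alone.
- A reader might take the single-failure sentence in Section 10.5 as a test result. It may express a clinical judgement, on which the binomial figures have no bearing.

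**Conclusion.** The concern holds for the missing measures of precision. SVR, failure, viremia and one-year survival have no interval, and the one planned test fails in the expected case. A report of 100% SVR would leave failure rates up to 23.2% (14 treated) or 41.0% (7 treated) unexcluded. These limits assume zero failures and an SVR result for every treated patient; Section 10 gives no rule for patients without the 3-month test.

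The viremia point is secondary. It concerns withdrawals, its size rests on an assumed dropout (70% against at most 77.8% with two censored), and weekly PCR to POW12 probably keeps it small. The 0% first-line failure expectation conflicts with the protocol's figure of at most 2%. That is an inconsistency to reconcile and does not establish a chronic-infection risk.

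**What to change.** - **Sections 10.4.1 to 10.4.3:** report SVR, treatment failure and viremia with Clopper-Pearson 95% intervals and delete the t-test. Report one-year survival by Kaplan-Meier with a 95% interval.
- **Section 10.2:** restate as an estimation aim. For example: to estimate SVR among treated recipients with an exact 95% interval; with no failures the lower limit would be 76.8% for 14 treated and 59.0% for 7.
- **Section 10.5:** reconcile 7 with 14 treated, and repair the wording of the 70% sentence.
- **Section 10.4.3:** beside the raw viremia percentage, give either a cumulative incidence with withdrawals censored and death as a competing event, or best- and worst-case counts.
- **Section 2.4.1:** reconcile the expected 0% first-line failure with the figure of 2% or less, keeping first-line failure apart from chronic infection after rescue.

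The cost is wording and a few lines of analysis. PCR dates and vital status are already collected, and no extra patients or tests are needed. The headline result will look less certain.

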10.4 Description of Statistical Methods

Since the anticipated study population will be a small size, statistical analyses will be limited to descriptive statistics. For patients who develop post-transplant viremia we will be able to compare our HCV cure rates to those that are expected for patients who receive treatment with these agents for chronic HCV.

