10.4.2 Analysis of the Primary Efficacy Endpoint(s)

The primary endpoint will be percentage of patients with sustained virologic response after treatment for HCV after lung transplant.

We expect that 100% of patients who are treated will achieve SVR. SVR will be defined as the absence of detectable HCV RNA Quantitative (PCR) testing 3 months after the completion of the treatment course. Any failure of therapy will be considered significant and will result in the halting of further enrollment until further discussed by the safety monitors and the IRB.

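### The planned t-test on the treatment-failure rate gives no valid result at zero failures and misses 3 to 4 failures of 14 (2 to 3 of 7) that an exact binomial test detects

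*Combined protocol and SAP*

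**What the plan says.** Section 10.4.1 ends its list of descriptive statistics with a significance test, the only one in the plan: "Comparison of treatment failure rates to expected treatment failure rates for the treatments used". The significance level is 0.05 and a "two-tailed t-test will be used". It does not say whether this is a one-sample or two-sample test, and it gives no numerical reference rate.

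Other sections supply the context:

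- **Reference rate.** Section 2.4.1 says of treatment failure from resistance: "In patients administered Mavyret, the risk of this was 2% or less". Section 10.5 reports efficacy of 98%, which implies a 2% failure rate.
- **Expected result.** Section 10.2: "We hypothesize that 100% of patients who develop HCV viremia will achieve SVR". That means zero failures.
- **Comparator.** Section 10.5: "This is a single-arm study with no comparison group".
- **Scope.** Section 10.4 says that "statistical analyses will be limited to descriptive statistics", although it also foresees comparing cure rates with those expected in chronic HCV.
- **Reading of one failure.** Section 10.4.2: "Any failure of therapy will be considered significant and will result in the halting of further enrollment". Section 10.5: "With an estimated 7 patients who will be treated, a single treatment failure will be regarded as a significant deviation from the expected outcome".

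**The concern.** A t-test estimates its standard error from the spread of the observed data. For 0/1 data with very few events, that spread is zero when there are no failures. Once failures occur it grows with their number, so a real excess inflates the yardstick it is measured against. The reference rate is fixed, so the exact binomial distribution is available and nothing needs approximating.

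The stake is what the report says about the primary endpoint, which section 4.2.1 says was chosen to evaluate safety. As written, the comparison either has no valid result or can describe a clear excess of failures as not significantly different from expected. The report would also use one word in two senses: a single failure is significant under 10.4.2 and 10.5, and not significant under the 10.4.1 test.

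**Working it through.** **Inputs**

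- Reference failure rate p0 = 0.02 (10.5: 98% efficacy; 2.4.1 gives 2% as an upper figure). Sensitivity value, an assumption: 0.01.
- Number treated, n. Section 10.5 gives 7, but its own 70% of 20 enrolled is 0.70 × 20 = 14. The two do not agree, so both are used.
- Two-sided alpha 0.05 (10.4.1).

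The plan states no power or p-value for this test, so there is no figure of its own to reproduce.

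**Formulas**, for k failures among n, with p̂ = k/n

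- One-sample t-test: SE = √[p̂(1 − p̂)/(n − 1)], t = (p̂ − p0)/SE, n − 1 degrees of freedom.
- Exact binomial, doubled tail: p = min(1, 2 × min[P(X ≤ k), P(X ≥ k)]), X ~ Bin(n, p0). The minimum-likelihood convention is shown as the alternative.

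**Zero failures.** Here p̂ = 0 and SE = 0, so t = −0.02/0, which has no valid p-value. Standard software (scipy) returns minus infinity and p = 0, which would read as a highly significant difference. If the true failure rate is 2%, zero failures has probability 0.98^14 = 0.754 or 0.98^7 = 0.868.

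**Worked case, 3 of 14**

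- t-test: p̂ = 0.2143, SE = √(0.2143 × 0.7857/13) = 0.1138, t = (0.2143 − 0.02)/0.1138 = 1.707 on 13 df, p = 0.112.
- Exact: P(X ≥ 3) = 1 − (0.7536 + 0.2153 + 0.0286) = 0.0025; doubled, 0.0049.
- Source of the gap: under the 2% reference the standard error is √(0.02 × 0.98/14) = 0.0374. The t-test uses a value about three times as large.

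**All relevant counts, p0 = 2%**

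| n | failures | t-test p | exact p, doubled tail | exact p, minimum likelihood |
|---|---|---|---|---|
| 14 | 1 | 0.484 | 0.493 | 0.246 |
| 14 | 2 | 0.228 | 0.062 | 0.031 |
| 14 | 3 | 0.112 | 0.0049 | 0.0025 |
| 14 | 4 | 0.054 | 0.00027 | 0.00014 |
| 14 | 5 | 0.025 | <0.0001 | <0.0001 |
| 7 | 1 | 0.423 | 0.264 | 0.132 |
| 7 | 2 | 0.200 | 0.016 | 0.008 |
| 7 | 3 | 0.090 | 0.0005 | 0.0003 |
| 7 | 4 | 0.034 | <0.0001 | <0.0001 |

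The t-test first rejects at 5/14 and 4/7. The doubled-tail exact test first rejects at 3/14 and 2/7 (2/14 by minimum likelihood).

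**Sensitivity to the reference rate.** The 4/14 result is borderline. Against 1%, the t-test gives 0.096 at 3/14 and 0.0465 at 4/14, while the doubled-tail exact p is 0.017 at 2/14. The t-test then misses 2 to 3 of 14. At n = 7 the thresholds stay at 4 and 2.

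**Power against 2%.** The true failure rates of 10% and 20% are illustrative assumptions; the plan gives none. All n patients are taken to be treated. For the t-test, k = 0 and k = n count as no rejection.

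| n | true rate | t-test | exact, doubled tail | exact, minimum likelihood |
|---|---|---|---|---|
| 14 | 10% | 0.9% | 16% | 42% |
| 14 | 20% | 13% | 55% | 80% |
| 7 | 10% | 0.3% | 15% | 15% |
| 7 | 20% | 3.3% | 42% | 42% |

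**The case against.** **The test may be two-sample.** Section 10.4.1 does not say one-sample, and section 2.2.2 mentions over 2300 trial patients and 98% SVR. Assume 46 failures in 2300 reference patients. A pooled-variance t-test then gives p = 0.59 at 0/14, detects 3 and 4 of 14, and gives p = 0.022 at 1/7, in line with 10.5 calling one failure significant. This shows that the plan underspecifies the test, but it does not rescue it. The plan names no reference sample for such a test, 10.5 says there is no comparison group and speaks of observed versus expected, and 10.4.5 says no comparison groups exist. That version also errs the other way: its 0.022 at 1/7 compares with an exact 0.26. A Welch version misses the same counts (0.112 and 0.054 at 3/14 and 4/14) and returns about 1e-11 at zero failures.

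**The affected counts are unlikely on the plan's own expectation.** This is true. At a 2% failure rate, 3 or more of 14 has probability 0.25% and 2 or more of 7 has 0.8%; at 5% they are 3.0% and 4.4%. But a test is there for the case where the expectation is wrong, and the zero-failure problem arises in the most likely case.

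**Halting makes fixed-n power unrealistic.** This stands as a limit on the power table. Section 10.4.2 halts further enrollment at any failure, so reaching 3 of 14 needs enrollment to resume or several failures among patients already enrolled. The p-values at given counts do not depend on this.

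**The effect is small in a descriptive pilot.** It is fair that no halting, sample-size or treatment decision uses this test and that the primary endpoint itself is a percentage. The plan nevertheless commits to a test and an alpha, and the p-value would be reported.

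**Conclusion.** The concern holds: the test is wrong as written and should be fixed. On the natural reading, one sample against a fixed 2%, it has no valid result at the hypothesised outcome. It also fails to flag 3 to 4 failures of 14 or 2 to 3 of 7, where doubled-tail exact p-values are at most 0.005 and 0.016 respectively. Using 7 or 14 does not change the conclusion. A 1% reference moves the missed range at n = 14 to 2 to 3 failures.

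The consequence is confined to the reported inference. Trial conduct is protected because any failure halts enrollment (10.4.2) and triggers an emergency meeting of the data and safety monitoring board (8.6), whatever the p-value. A single failure is not statistically significant under the t-test (0.42 at 1/7, 0.48 at 1/14) or the exact test (0.26 and 0.49, doubled tail), so that word in 10.4.2 and 10.5 cannot carry its statistical meaning.

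**What to change.** In 10.4.1, delete the t-test and adopt one of two options before any outcome data are analysed.

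- **(a) Preferred, and consistent with 10.4.** Report the treatment-failure and SVR percentages with exact Clopper-Pearson 95% confidence intervals beside a stated reference failure rate of 2% (SVR 98%), with no p-value. This works at zero failures: the failure interval is 0 to 23.2% for 0/14 and 0 to 41.0% for 0/7, which also shows how little a clean result rules out. For 3/14 it is 4.7 to 50.8%.
- **(b) If a test is kept.** Use an exact one-sample binomial test against a stated 2% with the doubled-tail p-value, so that test and Clopper-Pearson interval agree (2/14: p = 0.062, interval 1.8 to 42.8%, which includes 2%). Amend 10.4 to allow this single test.

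Under either option, state in 10.4.2 and 10.5 that calling a single failure significant does not mean statistical significance. The 7 and 14 in 10.5 should also be reconciled so that one denominator applies.

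Cost: one sentence in 10.4.1, one in 10.4 under option (b), and wording clarifications in 10.4.2 and 10.5. No extra patients or data are needed.
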